6.4.2. Additional considerations

6.4.2.1. Exclusion of implausible solicited Adverse Event

Some local and systemic adverse events will be directly measured by the subject and will not be subject to a reconciliation process, even if they are biologically implausible.

Statistical Analysis Plan

| | |
|--|--|
| Study alias & e-track number(s): V59 77 (205352) |  GSK |
| Version: 1 | Date: 19-09-2016 |

Therefore these implausible measurements will be removed from the analysis but included in listings. Implausible measurements are summarized in the table below:

Table 6.5.2.1-1: Implausible Solicited Adverse Events

| Parameter | Implausible measurements |
|------------------|---|
| Body temperature | $\leq 33^{\circ}\text{C}$ or $\geq 42^{\circ}\text{C}$ |
| Erythema | For subjects ≥ 6 years: ≥ 900 mm Measurements < 0 mm |
| Induration | For subjects ≥ 6 years: ≥ 500 mm Measurements < 0 mm |

6.4.2.2. **Solicited Adverse Events**

For details please refer to section 7.1.1 of the protocol.

Fever, defined as a body temperature of $\geq 38^{\circ}\text{C}$ irrespective of route of measurement, will be integrated to the summaries as a systemic adverse event.

The analyses will encompass summaries of the data on five levels:

1. Daily reports of subjects with solicited adverse events.
2. Time of first onset of solicited adverse events (excluding 30 min measurement).
3. Solicited adverse events, maximum event severity by event and interval [6h - day 3, day 4 -7, and 6h - day 7, each without 30 min].
4. Duration of solicited adverse events, including ongoing AE after Day 7.
5. Solicited adverse events and indicators of solicited adverse events, occurrence of at least one event by category (local, systemic) and interval 6h-Day 3, Day 4-7 and 6h-Day 7, each without 30 min].

For each of the time points or time intervals presented in the summaries, only subjects with at least one plausible observation (i.e., any non-missing values but excluding “Not done/unknown” and implausible values) for the solicited adverse events in the interval of interest will be considered. Subjects without plausible data (i.e. missing values or reported as “Not done/unknown” and implausible values) will be removed from the denominator to prevent a downward bias (towards zero).

Statistical Analysis Plan

| | | |
|--|------------|------------------|
| Study alias & e-track number(s): V59 77 (205352) | Version: 1 | Date: 19-09-2016 |
|--|------------|------------------|

 GSK GlaxoSmithKline

Level 1: Daily reports of solicited adverse event

For each of the time points (30 min, 6h, days 2, 3, 4, 5, 6 and 7) only subjects with at least one plausible observation (i.e., any non-missing values but excluding “Not done/unknown” and implausible values) for the solicited adverse event in the interval of interest will be considered. Subjects without plausible data (i.e. missing values or reported as “Not done/unknown” and implausible values) will be removed from the denominator in order to prevent a downward bias (towards zero). Data collected will be summarized (frequencies and percentages of subjects) by study group, solicited adverse event and time point.

Level 2: Time of first onset of solicited adverse events

The **time of first onset** is defined, for each subject, for each solicited adverse event, as the time point at which the respective solicited adverse event first occurred. For erythema, and induration the following threshold will be used: ≥ 25 mm. The summary will provide the frequencies and percentages of subjects with first onset of each solicited adverse events by study group and by each time point (30 min, 6h, days 2, 3, 4, 5, 6 and 7). Note, 'not done' is treated identical to 'missing'.

Level 3: Solicited adverse events, maximum event severity by event and interval

The **maximum event severity** will be defined if there is at least one plausible non-missing observation (excluding “Not done/unknown” and implausible values) within this time interval. Each subject’s data will be aggregated across the time points of the interval and summarized according to the maximal severity observed for each adverse event, followed by a summary across subjects for each vaccine. Subjects without any solicited adverse events in the interval, i.e., missing values at each of the requested time points, will be removed from the denominator.

Level 4: Number of days with solicited adverse events

The number of days with the adverse event is defined irrespective of severity. This means at least 'mild' solicited adverse event that are assessed qualitatively and ≥ 25 mm for erythema and induration. If a solicited adverse event continues beyond day 7 the period after day 7 is added.

| | | |
|--|------------|---|
| Statistical Analysis Plan | |  GlaxoSmithKline |
| Study alias & e-track number(s): V59 77 (205352) | Version: 1 | |

The frequency distribution of the number of days will be provided in a summary table by vaccine and by adverse event.

Level 5: Solicited adverse events, occurrence of at least one event by category (local, systemic) and interval.

The occurrence of at least one solicited adverse event is defined as “any” for a subject if he/she reports greater than “none” (≥ 25 mm, for erythema and induration) for the respective event and “none” otherwise. The occurrence of at least one solicited adverse event (i.e., none versus any) will be summarized by category (i.e., local, systemic, any), by study group and by time interval.

Medications to treat or prevent pain or fever will be summarized by frequencies and percentages of subjects reporting use of the medications by interval (30min, 6h - day 3, day 4 - 7, 6h - day 7).

Safety completeness analysis

The safety completeness analysis on solicited adverse events aims to identify subjects who completed diary cards, irrespective of severity. The analysis will show the number of subjects with *valid data* by solicited adverse event and time point. *Valid data* in the context of the safety completeness analysis are all data entered in the diary card (including implausible values) except “Not done/unknown”.

Four summaries will be produced:

1. The frequencies of subjects who provide diary cards by study group.
2. For each solicited adverse event, the frequencies of subjects with *valid data* will be presented by study group and timepoint: 30 min, 6h, days 2, 3, 4, 5, 6 and 7.
3. For each type of solicited adverse event (local, systemic) and indicators of solicited adverse events, such as analgesic use the frequencies of subjects with *valid data* by study group, aggregated over time points: 6h - day 7.
4. For each solicited adverse event, the frequencies of subjects with *valid data* by study group, aggregated over time points: 6h - day 7.

Statistical Analysis Plan

| | | |
|--|------------|------------------|
| Study alias & e-track number(s): V59 77 (205352) | Version: 1 | Date: 19-09-2016 |
|--|------------|------------------|

 GSK GlaxoSmithKline

For the corresponding percentages, the denominator will be the respective numbers of exposed subjects, i.e., subjects who received a vaccination and were still in-study for that time point or time interval, irrespective of whether a diary card was present or not.

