Reminder Phone calls: Two (2) reminder phone calls will be conducted at Day 3 and Day 5 after the study vaccination to remind the subject/legal guardian to complete the diary card.

Safety phone calls: Three (3) safety phone calls (at Day 15, Day 91 and Day 181) will be conducted to collect any medically-attended AEs, AEs leading to withdrawal, SAEs, related medications and any vaccinations. In addition, all unsolicited AEs and related medications occurring after the vaccination will be collected during the safety call at Day 15. The Day 181 Safety Phonecall will also serve as the termination visit.

Solicited Adverse Events (injection site pain, erythema, induration, fatigue, headache, myalgia, arthralgia, loss of appetite, nausea, chills and fever) occurring on the day of vaccination and the following six days (Day 1 through Day 7) will be recorded daily using a Diary Card for all subjects.

Unsolicited AEs occurring within 28 days after study vaccination will be collected. Qualified site staff will interview the subject by phone approximately 14 days after vaccination and in person at the study site approximately 28 days after study vaccination to assess the occurrence of any unsolicited AEs.

Medically-attended AEs AEs leading to study withdrawal and SAEs will be collected during the entire study period. These data will be captured by interviewing the subject and/or subjects' parents/ guardian (as applicable) during the sitevisits and phone calls and by review of available medical records. Subjects and/or parents / guardian will be encouraged to call the site in the event of any medically-attended AEs or any AEs which they perceive as being of concern during the entire study period.

Table 3.1-2: Schematic diagram of the V59_77 study design

Day 1	Day 4	Day 6	Day 15	Day 29	Day 91	Day 181
Blood draw (all subjects Menveo	Blood draw (50% of subjects)	Blood draw (50% of subjects)	Safety Phone call	Blood draw (all subjects)	Safety Phone call	Safety Phone call Study termination

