5.2.1 Post-vaccination Procedures

The following post-vaccination procedures will be performed on day 1.

- After vaccination, the subject will be observed for at least 30 minutes including observation for unsolicited adverse events, solicited adverse events, and body temperature measurement. Record **all** safety data collected during this time in the subject's source document.
- A Subject Diary will be used in this study to document solicited adverse events. The Subject Diary is the only source for collection of these data; therefore, it is critical that the subject completes the Subject Diary correctly. The subject should be trained on how and when to complete each field of the Subject Diary.
- The subject and/or parent(s)/legal guardian(s) should be trained on how to self-measure local solicited adverse events. The measurement of solicited local adverse events is to be performed using the ruler provided by the site.

- The subject and/or parent(s)/legal guardian(s) should be instructed how to perform body temperature measurement using the thermometer provided by the site. If the subject feels unusually hot or cold during the day, the subject and/or parent(s)/legal guardian(s) should check body temperature. If the subject has fever, the highest body temperature observed that day should be recorded in the Subject Diary.

Subject Diary training should be directed at the individual(s) who will perform the measurements of adverse events and who will enter the information into the Subject Diary. This individual may not be the subject and/or parent(s)/legal guardian(s), but if a person other than the subject and/or parent(s)/legal guardian(s) enters information into the Subject Diary, this person's identity must be documented in the Subject Diary or subject's source record. Any individual that makes entries into the Subject Diary must receive training on completion of the Subject Diary at the time of the visit. This training must be documented in the subject's source record.

The same individual should complete the Subject Diary throughout the course of the study.

- The site should schedule the next study activity clinic visit on Day 4 or Day 6 depending to which blood draw schedule subject was randomized to with the subject and/or parent(s)/legal guardian(s).

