Body temperature will be summarized separately according to the 3 schemes described below and will be broken down according to route of measurement:

- by 0.5 °C increments from 36.0°C up to ≥40°C;
- by 1°C increments: <36.0, 36.0-36.9, 37.0-37.9, 38.0-38.9, 39.0-39.9, ≥40°C;
- According to different cut-offs (< versus ≥): 38.0, 38.5, 39.0, 39.5, 40.0°C.

Statistical Analysis Plan

| | | |
|--|------------|------------------|
| Study alias & e-track number(s): V59 77 (205352) | Version: 1 | Date: 19-09-2016 |
|--|------------|------------------|

 GSK GlaxoSmithKline

Analysis of Unsolicited Adverse Events

This analysis applies to all adverse events occurring during the study, judged either as probably related, possibly related, or not related to vaccination by the investigator, recorded in AE CRF, with a start date on or after the date of first vaccination. AE starting prior to the first vaccination will only be listed. The original verbatim terms used by investigators to identify adverse events in the CRFs will be mapped to preferred terms using the MedDRA dictionary. The adverse events will then be grouped by MedDRA preferred terms into frequency tables according to system organ class (SOC).

All reported adverse events, as well as adverse events judged by the investigator as at least possibly related to study vaccine, will be summarized according to SOC and preferred term within SOC. These summaries will be presented by study group and by interval of study observation. When an adverse event occurs more than once for a subject, the maximal severity and strongest relationship to the vaccine will be counted.

Separate summaries will be produced for the following categories:

- Adverse events that are possibly or probably related to vaccine
- Unsolicited AEs reported within 30 minutes after vaccination
- Unsolicited AEs reported within 29 days after vaccination
- Adverse events leading to withdrawal
- Adverse events leading to a medically attended visit
- Serious adverse events

Data listings of all adverse events will be provided by subject. In addition, adverse events in the categories above will be provided as listed data.

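### Home temperature is requested on symptoms and recorded on fever, so dropping subjects with no reading from the denominator can inflate the fever percentage

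*SAP*

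**What the plan says.** **Measuring and recording.** Protocol 5.2.1 gives the only instruction on when to measure at home: "If the subject feels unusually hot or cold during the day, the subject and/or parent(s)/legal guardian(s) should check body temperature". The recording instruction follows: "If the subject has fever, the highest body temperature observed that day should be recorded in the Subject Diary". Nothing there asks for a reading from a subject who feels well, or for a normal value to be written down. At the clinic, the 30-minute observation applies to everyone, "including observation for unsolicited adverse events, solicited adverse events, and body temperature measurement". Protocol 3.4.2 has blank diary fields entered as missing.

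**Statements that point to daily recording.** Protocol 3.1 and SAP section 2 list fever among the solicited events and say that these "will be recorded daily using a Diary Card for all subjects". SAP 6.4.1 adds: "Body temperature will be summarized separately according to the 3 schemes described below". Two of those three schemes have bands below 38 °C.

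**Analysis.** SAP 6.4.2.2 defines fever as 38 °C or more by any route, which "will be integrated to the summaries as a systemic adverse event". At each time point or interval, only subjects with at least one plausible value for the event count. Subjects with none "will be removed from the denominator to prevent a downward bias (towards zero". The interval summaries exclude the clinic reading: "maximum event severity by event and interval [6h - day 3, day 4 -7, and 6h - day 7, each without 30 min". SAP 6.4.1 rules out imputation of missing safety data.

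**The concern.** The removal rule is sensible when a blank says nothing about whether the event occurred. A missing headache entry is of that kind. Temperature differs if 5.2.1 governs what subjects do: measurement is prompted by how the subject feels and recording by the result, so a blank will often come from someone who felt well. Removing the blanks then selects the denominator on the outcome. A rule meant to avoid bias toward zero would produce bias the other way.

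Solicited systemic events and body temperature are secondary safety endpoints (Protocol 8.1.2.1), reported as percentages by study group. At stake is whether the fever rows describe vaccinated subjects or mainly those who had a reason to use the thermometer.

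**Working it through.** The documents give no expected fever rate and no expected share of missing temperatures, so there is no planned figure to reproduce. The check concerns direction and a range.

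**Inputs**
- N = 300, the planned size of each primed group (Protocol 3.1).
- f, the true fever rate: assumed 1%, 2% or 5%.
- s, the probability that a febrile subject has a recorded reading: assumed 1.0, then 0.8.
- m, the same probability for an afebrile subject: assumed 1.0 down to 0.1.

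**Formula under the SAP rule**

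Reported rate = f·s / [f·s + (1 − f)·m]

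This exceeds f exactly when s > m. A symptom trigger would be expected to make s larger than m. If s = m, including the case where everyone records, there is no bias.

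**Every fever recorded (s = 1)**

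| m | f = 1% | f = 2% | f = 5% |
|---|---|---|---|
| 1.0 | 1.0% | 2.0% | 5.0% |
| 0.9 | 1.1% | 2.2% | 5.5% |
| 0.5 | 2.0% | 3.9% | 9.5% |
| 0.25 | 3.9% | 7.5% | 17.4% |
| 0.1 | 9.2% | 16.9% | 34.5% |

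For f = 2% there are 6 fevers and 294 afebrile subjects. At m = 0.9 the denominator is 6 + 264.6 = 270.6, and 6/270.6 = 2.2%. At m = 0.5 it is 6 + 147 = 153, and 6/153 = 3.9%. At m = 0.25 it is 6 + 73.5 = 79.5, and 6/79.5 = 7.5%. With all 300 as denominator the result is 6/300 = 2.0% in each case.

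**Some fevers missed (s = 0.8, f = 2%)**
- Recorded fevers: 6 × 0.8 = 4.8.
- All 300 as denominator: 4.8/300 = 1.6%, below the truth.
- SAP rule, m = 0.9: 4.8/(4.8 + 264.6) = 1.8%, also below the truth, because s < m.
- SAP rule, m = 0.5: 4.8/(4.8 + 147) = 3.2%, above it.

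**Which tables are exposed**
- Level 1 daily tables from 6 h to Day 7: exposed. The 30-minute point is not, since everyone is measured then.
- Level 3 intervals: exposed, because the 30-minute reading is left out. One reading on any day keeps a subject in, so 6 h to Day 7 should suffer less than the single days.
- Temperature tables in SAP 6.4.1: exposed in the same way.
- Level 5 is by category (local, systemic, any). A subject with any other plausible systemic entry is reasonably read as staying in, so it is largely unaffected.

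**The case against.** The strongest reply is that 5.2.1 adds a prompt for extra readings and does not describe the whole scheme. It does not confine measurement to subjects who feel hot or cold. Daily recording is stated for all subjects with fever on the list, subjects are trained on when to complete each diary field, and reminder calls are planned for Days 3 and 5. The SAP allows for a not-done or unknown response, which suggests a scheduled entry, and it plans bands for normal temperatures. The diary card is not among the documents. If it asks for a temperature each day, most afebrile subjects may have a reading and the inflation would be small, about 1.1-fold at m = 0.9.

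That stands, and it makes the bias conditional. It does not settle which instruction sites will follow, since the daily statements never mention taking a temperature in a subject who feels well.

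The safety completeness analysis in SAP 6.4.2.2 also counts valid entries by event, group and time point over all exposed subjects still in the study. This would show how many temperatures are missing, but it would leave the fever percentage as it is. Safety is descriptive, with no planned statistical comparison between groups, so no confirmatory conclusion depends on this rate.

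**Conclusion.** The plan contains an unreconciled instruction which, if followed literally, makes the fever denominator depend on the outcome. The bias is upward on the condition that febrile subjects are likelier than afebrile ones to have a reading. Its size cannot be fixed from the documents: at an assumed 2% true rate with all fevers recorded, it runs from none when everyone records to 3.9% at half and 7.5% at a quarter of afebrile subjects recording. The primary immunogenicity objective is untouched.

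A reader might infer more than this:
- **That temperature is taken only on symptoms, so the reported rate is certainly inflated.** The protocol does not say so, and the s = 0.8, m = 0.9 case gives a rate below the truth.
- **That group differences in fever would be artefacts.** This needs recording habits to differ between groups, and nothing in the documents shows that they would.
- **That an absent reading should count as no fever in the main table.** This conflicts with the no-imputation rule and understates the rate if fevers go unmeasured.

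**What to change.** 1. **Protocol 5.2.1 and the diary training.** Reconcile the symptom-triggered wording with the daily-diary statements: subjects record temperature once daily on Days 1 to 7 whatever the value, plus the highest value if they measure more than once. Subjects already receive a thermometer and a daily diary, so the cost is a line of instruction and one more entry per day.

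2. **SAP 6.4.2.2.** Keep the measured-only fever table. Add a second whose denominator is all subjects with any diary entry in the interval, showing the number with a temperature. Label it a lower bound, because unmeasured fevers count as none, and state that this is a supplementary departure from the no-imputation rule. The cost is a sentence and one extra table. The two tables should be read with the number measured, because they need not bracket the truth: in the s = 0.8, m = 0.9 case they give 1.8% and 1.6% against a true 2%.

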6.4.2.3. Unsolicited Adverse Events

All AEs occurring during the first 28 days after vaccination, including the day of vaccination, and all medically attended unsolicited adverse events, adverse events leading to study withdrawal and serious adverse events occurring at any time during the study will be recorded according to the protocol-specified reporting rules.

Only vaccine-emergent adverse events (see [section 11.2](#) for definition) will be analyzed, i.e., excluding those after a subject has given informed consent but before vaccination. The selection of unsolicited adverse events and the assignment to time intervals will be done by day of onset and not by days ongoing/persisting.

The analysis of unsolicited adverse events comprises the following categories:

- Any unsolicited adverse event.
- Possibly or probably related unsolicited adverse events.
- Unsolicited adverse events leading to death.
- Serious adverse events.
- Possibly or probably related serious adverse event.
- Unsolicited adverse events leading to premature withdrawal from study.
- Unsolicited adverse events leading to hospitalization.
- Medically attended adverse events.

Solicited adverse events continuing beyond day 7 will be coded by MedDRA and combined with the respective unsolicited adverse events.

6.4.2.4. Combined Solicited and Unsolicited Adverse Events

A summary of subjects with all combined solicited (regardless of their duration) and unsolicited adverse events will be provided. Solicited adverse events will be coded by MedDRA as per the following codes:

| Statistical Analysis Plan | |  GlaxoSmithKline | |
|--|------------------|---|--|
| Study alias & e-track number(s): V59 77 (205352) | | | |
| Version: 1 | Date: 19-09-2016 | | |

| Solicited symptom | Lower level code | Lower level term |
|-------------------|------------------|---------------------------|
| Pain | 10022086 | Injection site pain |
| Fever | 10016558 | Fever |
| Loss of appetite | 10003028 | Appetite lost |
| Erythema | 10022061 | Injection site erythema |
| Induration | 10022075 | Injection site induration |
| Fatigue | 10016256 | Fatigue |
| Headache | 10019211 | Headache |
| Myalgia | 10028411 | Myalgia |
| Arthralgia | 10003239 | Arthralgia |
| Nausea | 10028813 | Nausea |
| Chills | 10008531 | Chills |

For clinicaltrials.gov and EudraCT posting purposes, a summary of combined solicited and unsolicited non-serious adverse events will be produced by System Organ Class and according to occurrence of each event.

